3.2. Study Schematics

Figure 3 Overall Study Design

[figure not shown]
[figure not shown]

Figure 4 Study Visits Schematic

For study assessments see the Time and Events tables in Section 6.2

Note: Dosing on Days 4-6 inclusive may be performed on an out-patient basis, if judged acceptable on the basis of the clinical condition of the patient by the Investigator.

3.3. Discussion of Study Design

3.3.1. Design Rationale

3.3.1.1. Study Population

The study population is chosen to replicate the demographics of patients who showed least decline in β -cell function based on *post hoc* sub-group analyses in Phase II (BDR) and Phase III (Defend 1 & 2) studies with oteelixizumab. See Section 4.2.1 for full inclusion criteria. Patients of paediatric age (16 and 17 years old) will be included as there is a high prevalence of the disease in this age group.

3.3.1.2. Study Duration

Data from the literature at the origin of the study design identified a causal relationship between the degree of immunosuppression and an increased incidence of EBV related Post Transplant Lymphoproliferative Disorders (PTLD) and for this reason a long-term follow-up (60 months) was implemented at the start of the study. The interim analysis data which emerged from this study showed a prompt regain of immune competence observed in treated subjects and consequent rapid resolution of EBV reactivation, both clinically and virologically. The long term EBV related PTLTD risk, as observed in solid organ transplant on a chronic immune suppression therapy, is negligible. As a result, the overall study duration for each subject will be 24 months, except for those patients who have already passed the 24 month or 36 month follow up, in which case they will have a final follow up communication (telephone call or visit) as soon as possible following approval of this amendment 08 of the protocol. Further details are provided in the Study Reference Manual (SRM). If further follow up is required, the Investigator will request that the patient visits the site. See Section 9.3 for a description of analysis considerations.

3.3.1.3. Measurement of beta cell mass and function, disease progression and predictive biomarkers

The assessment of the number and function of β -cells *in vivo* is necessarily indirect and based on static or dynamic measures of the concentration of β -cell products in the peripheral circulation. An international D-Cure workshop in 2007 recommended the measurement of stimulated C-peptide under standardised conditions, and particularly the 2-h area under the curve (AUC) during a mixed meal tolerance test (MMTT) as the primary endpoint in interventional trials evaluating therapies aimed at preserving or improving β -cell function in T1DM [Cernea, 2009]. The MMTT test has been validated to assess β -cell function by measuring residual C-peptide secretion as an appropriate outcome for therapeutic trials in early T1D [Greenbaum, 2008]. Validated measures of β -cell function from the MMTT test include fasting and 2-h insulin and C-peptide levels, and the calculated AUC for each analyte during the test. Further parameters are generated by a mathematical model of β -cell function and insulin secretion rate (ISR) calculated by deconvolution analysis of C-peptide levels, and β -cell glucose sensitivity [Mari, 2008]. Both peak C-peptide response and the C-peptide AUC during the MMTT test are highly reproducible and validated against the Glucagon Test [Greenbaum, 2008].

By assessing β -cell function after MMTT, some estimate of the rate of decline of β -cell mass can be made. The majority of the data have been derived from the control/placebo arm of interventional studies and likely reflects disease progression in patients whose insulin therapy has been optimized. Recent studies employing MMTT at baseline, 3, 6, 9 and 12 months post randomization in patients recruited within 3 months of diagnosis report an approximate linear decline in C-peptide AUC over the period from 3-12 months [Herold, 2002, Herold, 2005, Sherry, 2011]. In some of these studies, the initial rate of decline of β -cell loss in these studies (over the period from baseline to 3 months) is reduced in the control patients (or even increased above baseline) and this has been attributed to the effects of tighter glycaemic control reducing the possible toxic effects of hyperglycaemia and dyslipidaemia on β -cell function.

A two-phase glucose-clamp procedure will be also performed at baseline and 6 and 24 months post-treatment (-180 to 0 minutes), when euglycemia (60-90 mg/dl) will be maintained by intravenous insulin infusion to keep low endogenous insulin secretion and during the second phase (0 to 140 minutes), blood glucose levels will be increased and maintained between 180-240 mg/dl in order to test and stimulate the endogenous residual β -cell secretory capacity. This methodology which has been used in previous studies [Keymeulen, 2005] should allow us to characterize the second phase of insulin secretion (+60/+140 min post start of Hyperglycaemic Phase) with a lower degree of intra and inter-individual variability in comparison with the MMTT.

3.3.2. Dose Rationale

The proposed daily and cumulative doses and duration of treatment in this study are supported by the existing clinical safety data obtained in the original proof of concept study in NOT1DM patients (BDR study), where 6 day regimens of short daily infusions of 8 mg, and individual daily doses of up to 24 mg, were investigated (cumulative dose 48-64 mg).

The mechanism of action of anti-CD3 mAb therapy and the degree and duration of pharmacology necessary for clinical benefit is not fully understood. However, the weight of clinical evidence obtained in NOT1DM patients, based on the cumulative experience with oteelixizumab and teplizumab (see Section 1.2), suggests a high degree of CD3 target engagement and thus a relatively low level of free CD3 antigen on peripheral blood T-lymphocytes (<10%) during the dosing period may be required to achieve a demonstrable effect on stimulated C-peptide secretion and insulin production. In addition, this level of blockade was required for effective inhibition of a range of human lymphocyte proliferative responses *in vitro* - see the Investigators Brochure. The lowest proposed dosage regimen (9 mg total dose) is anticipated to maintain an average of ~ 10% free CD3 antigen on peripheral blood T-lymphocytes during the dosing interval. Higher doses are anticipated to reduce free CD3 to less than 10% for the entire dosing period. A 6 day dosing regimen, as used in the BDR study where efficacy was demonstrated, was also chosen for this study.

The majority of all reactions, and all severe infusion-reactions with oteelixizumab in the BDR study occurred during the first 3 days of treatment [Keymeulen, 2005]. In the TTEDD study, when the infusion time was reduced from 2 hours to 30 or 15 mins, there was a corresponding increase in both peak serum cytokine levels and the incidence of CRS-related adverse events.

An overview of the regimens proposed for each cohort is presented below in Table 1. The slow infusions for the first three days of treatment are anticipated to improve the tolerability associated with administration of oteelixizumab relative to the short infusion regimens investigated in previous studies.

Table 1 Dosage Cohorts

Cohort	Cumulative Dose (mg)	Day 1			Day 2			Day 3			Days 4-6		
		D (mg)	R (mg/h)	T. (h)	D (mg)	R (mg/h)	T. (h)	D (mg)	R (mg/h)	T. (h)	D (mg)	R (mg/h)	T. (h)
1	9	1.5	0.167	9*	1.5	0.25	6	1.5	0.5	3	1.5	1.5	1
2	18	3	0.25	12	3	0.5	6	3	1	3	3	3	1
3	27	4.5	0.375	12	4.5	0.75	6	4.5	1.5	3	4.5	4.5	1
4	36	6	0.5	12	6	1.2	6	6	2	3	6	6	1

NB: D = daily dose, R = rate of infusion, T = infusion time or duration

* The 9mg (Cohort 1) infusion time will be 9 hours on Day 1

If there is any need to reduce the infusion rate or temporarily stop the infusion, the Investigator should first consult with the Medical Monitor who will consult with the Sponsor. However, the Investigator has the flexibility to reduce or temporarily stop the infusion immediately (with no prior consultation with the Medical Monitor), if there are any immediate safety/tolerability concerns. In this case the Investigator must inform the Medical Monitor as soon as possible after reducing or stopping the dosing.

3.4. Risk Management

Table 2 Summary of Key Issues, their Impact and Strategy to Mitigate Risk

Potential Risk	Summary of Data	Impact- Eligibility Criteria	Strategy-Monitoring/Stopping Criteria
Cytokine Release Syndrome (CRS) (chills/rigors, fever, nausea, vomiting, diarrhoea, arthralgia, myalgia, hypotension, headache)	
 CRS is a well-known consequence of anti-CD3 therapy when administered via intravenous injection or infusion. Additionally, with high doses of oteixizumab (e.g. 48-64mg cumulative tested in the BDR study), liver enzyme elevations occurred and were considered to be possibly associated with CRS. 	
Patients with on-going pyrexial infections and with history of significant systemic infection during the 6 weeks prior to the first dose of study drug will not be enrolled.
 
Only patients with normal liver function will be included, defined as AST or ALT >2.0 ULN
	
 Slow infusion; The infusion of the first dose in each cohort will be conducted over 12 hours. (except for cohort 1 which will last 9 hours). The reduction of the infusion time will be staged. Inpatient clinical observation; at a minimum, patients will be in-house for the first 3 days of the infusion period. Days 4, 5 & 6 may be on an out-patient basis with safety monitoring for at least 3 hours post dose. Patients will be discharged only after Investigator clinical approval. The facilities will be located within a hospital with provision for Intensive Care facilities and with immediate access to resuscitation and emergency care. Prophylaxis CRS; prophylaxis (see Section 5.10.1) will be administered in conjunction with adequate oral hydration prior to and during dosing with oteixizumab Withdrawal and stopping criteria; Individual withdrawal criteria are in place (see Section 5.3). Dose Escalation: dose escalation is based on a strict CRS AE criteria (see Section 5.3)

Potential Risk	Summary of Data	Impact- Eligibility Criteria	Strategy-Monitoring/Stopping Criteria
Allergic hypersensitivity reactions	
 • Allergic hypersensitivity reactions to biologics are relatively common and in practice may be difficult to differentiate from CRS. • Allergic/hypersensitivity reactions may include the following: flushing, pruritus, rash, hives, bronchospasm, dyspnea, diaphoresis, abdominal cramping. • Angioedema, rash, including urticaria, was seen in orelizumab studies in patients with T1DM. No anaphylaxis or anaphylactoid reactions have been seen to date. 	Patients with prior allergic reaction, including anaphylaxis, to any human, humanised, chimeric, or rodent antibody will not be enrolled.	
 • An anti-histamine given as part of CRS prophylaxis may decrease the occurrence of rash. • Medical management of more severe allergic reactions as per local clinical guidelines • Individual withdrawal criteria and Study stopping criteria are in place (see Section 5.3)

Potential Risk	Summary of Data	Impact- Eligibility Criteria	Strategy-Monitoring/Stopping Criteria

Epstein-Barr virus (EBV)
	
 • Epstein-Barr virus (EBV) is a widespread human gamma herpes-virus. • Primary infection with EBV usually occurs asymptotically, where after the virus persists for life in a latent form in B lymphocytes. • The initial expansion and reactivation of these latently infected B lymphocytes is controlled by specific CD8+ major cytotoxic T-lymphocyte (CTL) responses. • EBV reactivation is accompanied by one or more of the following: rash; elevated liver function tests, other signs and symptoms consistent with acute infectious mononucleosis (pharyngo-laryngeal pain, acute tonsillitis, lymphadenopathy, fever). • The most sensitive confirmation of EBV reactivation is by detecting an increase in viral copy number (by RT-PCR). • In patients on chronic immune-suppression persisting EBV reactivation can be detected. Chronic EBV reactivation is thought to be causal for early post-transplant lymphoproliferative disorder (PTLD) which may occur in up to 30-40% of patients chronically maintained on high dose immunosuppression. • In studies with otelexizumab in patients with NOT1DM an increased incidence of transient EBV reactivation with regimens employing higher daily doses has been observed (i.e. 48-64mg cumulative tested in the BDR study). Rapid immune response was evident and full immunity to EBV was restored with no evidence of recurring viremia. Maximum EBV levels occurred around Week 3 and decreased to baseline around Month 3. • As daily dose increases, so the degree of lymphopenia increases and TCR/CD3 surface expression declines, resulting in approximately 90% reduction in surface expression of TCR/CD3 of 90% sustained. 	
Patients within 3 months of evidence of acute/active EBV infection (e.g)
 
 • Symptomatic • Positive EBV capsid Ab IgM in absence of a positive EBV EBNA Ab IgG • EBV viral load of >10,000 copies per 10⁶ lymphocytes 
will not be enrolled in the study.
	
 • Patients with previous history of immunosuppression and/or on active immunosuppressant therapy will be excluded from this study • Patients will be monitored for clinical symptoms of mononucleosis and changes in EBV viral load.

Potential Risk	Summary of Data	Impact- Eligibility Criteria	Strategy-Monitoring/Stopping Criteria
Abnormal Liver Chemistry	
 In the Belgian Diabetes Registry study, administration of high cumulative doses of oteixizumab (48-64mg) have been temporally associated with abnormal liver chemistry thought to be due to increased cytokine release. In subsequent dose-finding studies conducted at lower doses, no trends with respect to changes in liver chemistry were observed. 	Patients with history of liver diseases and/or persistent AST or ALT >2.0 ULN will not be included	Liver chemistry will be monitored daily for the duration of treatment to detect any unanticipated liver event. Liver chemistry individual withdrawal and study stopping criteria and follow-up are in place (Section 5.3).
Progressive Disease			Intensive monitoring and care will be provided according to current standards of care for patients with type 1 diabetes. Diabetes care will be at the discretion of the investigator and may include consultations with a nutritionist or dietician and/or a diabetes educator according to the local institution's guidelines for NOT1DM. Study centres are expected to work with each subject to optimize glycaemic control as per standard of care, with a target HbA1c less than 7% (53 mmol/mol). HbA1c will not be communicated to the trial centre by BDR unless HbA1c is $\geq 7\%$. Diabetes management will be directed towards helping each subject reach this target or come as close to it as possible.

4. STUDY POPULATION

4.1. Number of Subjects

Approximately 40 subjects will be enrolled into the study in order to have 10 patients complete dosing on all four cohorts (stopping criteria permitting). Ten (10) subjects will be enrolled in each cohort, 8 on otelixizumab and 2 on placebo (4:1 ratio). Each cohort will comprise a new set of subjects.

If subjects prematurely discontinue the study, additional subjects may be enrolled as replacement subjects and assigned to the same treatment at the discretion of the Sponsor in consultation with the Investigator.

The decision whether to replace the patient will be based on the reason for premature discontinuation (see Section 4.5 for further information).

Replacement subject numbers will be assigned to the additional subjects.

4.2. Eligibility Criteria

Specific information regarding warnings, precautions, contraindications, adverse events, and other pertinent information on the GSK investigational product or other study treatment that may impact subject eligibility is provided in the Investigator Brochure.

Deviations from inclusion and exclusion criteria are not allowed because they can potentially jeopardize the scientific integrity of the study, regulatory acceptability or subject safety. Therefore, adherence to the criteria as specified in the protocol is essential.

4.2.1. Inclusion Criteria

A subject will be eligible for inclusion in this study only if all of the following criteria apply:

1. Male or female aged between 16 and 27 years of age inclusive, at the time of signing the informed consent.

NOTE: Subjects aged 16 to 17 years must be Tanner Stage ≥ 2 (see SRM). All subjects must weigh at least 31 kg.

2. Diagnosis of diabetes mellitus according to ADA and WHO criteria and consistent with Type 1a (autoimmune) DM, with an interval of approximately 28 days (not more than 32 days) between the initial diagnosis and the first dose of study drug). Written documentation of the diagnosis of DM, including the date of diagnosis, must be obtained from the diagnosing physician.
3. Currently requires insulin treatment for T1DM and has received insulin therapy for at least 7 days prior to screening.
4. Positive for at least one autoantibody associated with T1DM: antibody to glutamic acid decarboxylase (anti GAD), antibody to protein tyrosine phosphatase-like protein (anti IA 2), antibody to islet-cell antigen (ICA) or ZnT8 Autoantibody.

5. Evidence of residual functioning β cells as measured by mixed meal stimulated C-peptide peak level ≥ 0.2 nmol/L.
6. A female subject is eligible to participate if she has a negative pregnancy test as determined by a serum hCG test at screening or prior to dosing AND
 - Agrees to use one of the contraception methods listed in Section 4.3.1. Female subjects must agree to use contraception for 2 weeks prior to dosing and for 60 days after the last dose of study drug.
 - OR has only same-sex partners (refrains from heterosexual intercourse), when this is her preferred and usual lifestyle.
7. Male subjects with female partners of child-bearing potential must agree to use one of the contraception methods listed in Section 4.3.1. This criterion must be followed from 2 weeks prior to dosing and for 60 days after the last dose of study drug.
8. Willing to follow the procedures outlined in the protocol.
9. AST and ALT $<2xULN$; alkaline phosphatase and bilirubin $\leq 1.5xULN$ (isolated bilirubin $>1.5xULN$ is acceptable if bilirubin is fractionated and direct bilirubin $<35\%$).
10. Subjects eligible for enrolment in the study must meet all of the following criteria:
 - QTc <450 msec *or*
 - QTc <480 msec for patients with bundle branch block

The QTc is the QT interval corrected for heart rate according to either Bazett's formula (QTcB), Fridericia's formula (QTcF), or another method, machine or manual overread.

- For subject eligibility and withdrawal, QTcF will be used.
- For purposes of data analysis, QTcF will be used as primary.

The QTc should be based on single or averaged QTc values of triplicate electrocardiograms (ECGs) obtained over a brief recording period.

11. Screening total lymphocyte counts within the normal range in two separate samples taken at least three days apart (eg screening and Day -1).
12. Capable of giving written informed consent, which includes compliance with the requirements and restrictions listed in the consent form. In the case of minors (under 18 years) written informed consent must also be obtained from a parent or Legally Acceptable Representative (LAR).

4.2.2. Exclusion Criteria

A subject will not be eligible for inclusion in this study if any of the following criteria apply:

1. A positive pre-study Hepatitis B surface antigen or core antibody or positive Hepatitis C antibody result within 3 months of screening.

2. Current or chronic history of liver disease, or known hepatic or biliary abnormalities (with the exception of Gilbert's syndrome or asymptomatic gallstones).
3. A positive test for HIV 1 and/or 2 antibody.
4. The subject has participated in a clinical trial and has received an investigational product within the following time period prior to the first dosing day in the current study: 30 days, 5 half-lives or twice the duration of the biological effect of the investigational product (whichever is longer).
5. Exposure to more than four new investigational drugs within 12 months prior to the first dosing day.
6. History of sensitivity to any of the study medications, or components thereof or a history of drug or other allergy that, in the opinion of the investigator or CRO/GSK Medical Monitor, contraindicates their participation.
7. Where participation in the study would result in donation of blood or blood products in excess of 500 mL within a 3 month period.
8. Lactating females.
9. Subject is mentally or legally incapacitated.
10. History of thrombocytopenia.
11. The subject has received immunization with a vaccine within 4 weeks before the first dose of study drug or requires a vaccine within 30 days after the last dose of study drug
12. The subject has had significant systemic infection during the 6 weeks before the first dose of study drug (e.g., infection requiring hospitalisation, major surgery, or i.v. antibiotics to resolve; other infections, e.g., bronchitis, sinusitis, localised cellulitis, candidiasis, or urinary tract infections, must be assessed on a case-by-case basis by the investigator regarding whether they are serious enough to warrant exclusion).
13. Current or prior malignancy, other than non-melanoma skin cancer.
14. Patient has undergone a splenectomy
15. Radiological evidence of active tuberculosis (TB).
16. Significant and/or active disease in any body system likely to increase the risk to the subject or interfere with the subject's participation in or completion of the study. Examples of significant diseases include, but are not limited to, coronary artery disease, congestive heart failure, uncontrolled hypertension, renal failure, emphysema, history of bleeding peptic ulcers, history of seizure(s), addiction to illicit drugs, and alcohol abuse.
17. Clinically significant (based on Investigator's discretion in consultation with the Medical Monitor if second opinion required) abnormal laboratory values during the screening period, other than those due to T1DM. A clinically significant abnormal value will not result in exclusion if, upon retest, the abnormality is resolved or becomes clinically insignificant.
18. Positive EBV capsid Ab IgM in absence of a positive EBV EBNA Ab IgG

19. EBV viral load of $>10,000$ copies per 10^6 peripheral blood mononuclear cells (PBMCs) as determined by quantitative polymerase chain reaction (qPCR)..
20. IgG negative for EBV.
21. A positive result on a test for syphilis; and if result of the first test is positive, then a confirmatory test using another method will be performed.
22. Have used any atypical antipsychotic drug (e.g., risperidone [Risperdal], quetiapine [Seroquel], or clozapine [Clozaril]) within the 30 days before signing the ICF.
23. Have previously received orelizumab or any other anti CD3 monoclonal antibody, e.g., OKT3 (muromonab or Orthoclone), ChAglyCD3, or hOKT3 γ 1 (ala ala), and are not willing to refrain from using any such antibody for the planned duration of study participation (2 years after the last dose of study drug).
24. Previous or current exposure to biologic cell-depleting therapies (e.g. anti-CD11a, anti-CD22, anti-CD20, anti-BLyS/BAFF, anti-CD3, anti-CD5, anti-CD52) including investigational agents, and planning to use any such antibody for the planned duration of study participation (2 years after the last dose of study drug).
25. Predisposition to thromboembolic disease, or thromboembolic event (excluding superficial) in the past 12 months.
26. Is currently receiving corticoid treatment or has received systemic corticoid treatment within a month of screening.
27. History of Graves disease
28. Prior allergic reaction, including anaphylaxis, to any human, humanised, chimeric, or rodent antibody.
29. Have undergone any major surgical procedure within 30 days before the first dose of study drug, and/or planning to undergo any such surgery within 3 months after the last dose of study drug.
30. Any condition or situation that, in the investigator's judgment, is likely to cause the subject to be unable or unwilling to participate in study procedures or to complete all scheduled assessments.

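### Exclusions 23 and 24 join past exposure and future intent with 'and', so a patient previously given an anti-CD3 or cell-depleting antibody who does not intend further use is not excluded as written

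*Protocol*

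**What the plan says.** Section 4.2.2 opens with the rule that governs the list: "A subject will not be eligible for inclusion in this study if any of the following criteria apply". One criterion is enough to exclude, but that criterion has to be met.

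- **Exclusion 23** starts with past exposure, "Have previously received orelizumab or any other anti CD3 monoclonal antibody", and continues "and are not willing to refrain from using any such antibody for the planned duration of study participation", with the period given as 2 years after the last dose.
- **Exclusion 24** starts with "Previous or current exposure to biologic cell-depleting therapies". Its examples include anti-CD3. It continues "including investigational agents, and planning to use any such antibody for the planned duration of study participation", over the same period.
- **Exclusion 29** pairs major surgery in the 30 days before dosing with a future plan, joined as "and/or planning to undergo any such surgery within 3 months after the last dose of study drug".
- **Section 3.4, Table 2, EBV row**, under monitoring and stopping strategy: "Patients with previous history of immunosuppression and/or on active immunosuppressant therapy will be excluded from this study".

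Section 4.2 allows no deviations from the criteria and calls adherence to them as specified essential.

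**The concern.** A site that applies exclusions 23 and 24 as written has no ground in either one to refuse a patient who has already had otelixizumab, muromonab or another listed antibody, provided the patient does not intend more. Section 4.2 leaves the site no room to apply a presumed intention instead.

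The protocol's own background shows why prior exposure could matter here:

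- Section 1.2.4 says muromonab is associated with infusion reactions and neutralising antibodies. Events related to cytokine release are part of the primary endpoint, and change in anti-drug antibodies is a secondary endpoint.
- Section 1.2.5 describes C-peptide differences lasting up to 2 years after teplizumab, and a reduced insulin dose for up to 4 years in a subset given otelixizumab. A lasting effect from earlier treatment would blur the 24-month efficacy comparisons.
- Section 1.2.4 lists trials of these antibodies in ulcerative colitis, psoriasis and arthritis, so exposure before a diabetes diagnosis is possible.

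With 8 active and 2 placebo patients per cohort, there is little to dilute one atypical patient.

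**Working it through.** The plan gives no figure to reproduce. The check is logical: what each criterion excludes, then whether anything else in the protocol excludes the same patient.

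**Step 1. The four combinations.** Let A be past exposure (previous or current in exclusion 24) and B be future intent (unwilling to refrain in 23, planning use in 24).

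| A | B | Excluded with 'and' (as written) | Excluded with 'and/or' |
|---|---|---|---|
| yes | yes | yes | yes |
| yes | no | **no** | yes |
| no | yes | **no** | yes |
| no | no | no | no |

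As written, each criterion excludes 1 of 4 combinations. With 'and/or' it would exclude 3 of 4.

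**Step 2. The two criteria together.** Anti-CD3 appears in both, so a patient with prior anti-CD3 treatment passes both only if willing to refrain and not planning further use. For a cell-depleting antibody of another kind, only exclusion 24 applies, and having no plan for further use is enough to pass.

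**Step 3. Is 'and' just loose drafting for 'or'?** The grammar of both sentences attaches the second part to the same patient. Exclusion 29, in the same list, uses 'and/or' for the same past-and-future pairing, and exclusions 11 and 26 use 'or' where either part should exclude. The list therefore makes the distinction elsewhere.

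**Step 4. Does another provision close the A-yes, B-no gap?**

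- *Exclusion 4* covers investigational products only, within the longest of 30 days, 5 half-lives or twice the duration of biological effect. Exclusion 24 speaks of therapies including investigational agents, so it is meant to reach beyond those, and exclusion 4 is not.
- *Exclusion 28* covers only patients with a prior allergic reaction to an antibody.
- *Exclusion 30* concerns ability and willingness to complete the study.
- *Table 2* speaks of past immunosuppression generally, names none of these antibodies and has no counterpart among the numbered criteria.

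None excludes past exposure as such.

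**Step 5. Does another provision cover the A-no, B-yes case?** Partly. Section 5.11 says patients should not receive potent immunosuppressive agents during the study. Its list of examples is open, and it adds a 24-month restriction without saying from what point. It does not name anti-CD3 antibodies and is not an eligibility rule, but it does address later use.

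**Step 6. Would the analysis show such a patient?** SAP Section 4.1 builds the inclusion/exclusion deviation summary from the inclusion/exclusion form. An A-yes, B-no patient breaches neither criterion as written, so the form would record no deviation from them.

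**Size.** One such patient in an active arm is 1/8 = 12.5% of it. The documents give no frequency for prior exposure.

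**The case against.** The strongest reply is that the gap is nearly empty. Patients are 16 to 27 and are dosed within 32 days of diagnosis, so earlier treatment in a new-onset diabetes trial is practically ruled out. Exclusion 4 may reach far back: if the duration of biological effect were taken from the 12 to 18 months in Section 1.1 or the 4 years in Section 1.2.5, twice that is 24 to 36 months, or 8 years. A transplant patient given muromonab would very likely be caught by Table 2 if a site applied it. Anti-drug antibodies are sampled on Day -1, so pre-existing ones would be visible. All of this stands as a reason to expect few cases. It does not repair the criteria: the protocol does not define duration of biological effect for exclusion 4, and that exclusion does not reach treatment outside trials.

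Four stronger readings are tempting and should not be drawn:

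- *Every previously treated patient is eligible.* No: those who are unwilling to refrain, or who plan further use, are excluded.
- *Table 2 directly contradicts the criteria.* Its 'and/or' joins past immunosuppression with active therapy, not past exposure with future intent, and it names none of these antibodies. It is an inconsistency to reconcile.
- *Later use is uncontrolled.* Section 5.11 partly controls it.
- *One exposed patient supplies one third of the 3-of-8 stopping count.* That holds only if the patient also meets a stopping criterion, which nothing in the documents establishes.

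**Conclusion.** The point holds for exclusions 23 and 24 as written. The gap that matters is past exposure without future intent. The unexposed patient who plans such treatment also passes both criteria, but Section 5.11 makes that case weaker. The likely number of affected patients is small, possibly none; that is a judgement from the age range and the 32-day limit, since the documents give no count. A reader might infer that such a patient was enrolled. Nothing in the documents says so.

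The conclusion rests on reading 'and' in its ordinary sense, supported by the contrast with exclusion 29, and on the absence of any other criterion that excludes past exposure as such. The case for acting is that an operative eligibility rule does not exclude on past exposure alone, and that the standard deviation output cannot reveal the consequence. SAP Section 2.3 records that the escalation stopping criteria were met in Cohort 3, so the practical interest now lies more in checking who was enrolled than in protecting future recruitment.

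**What to change.** 1. **Wording.** The sponsor should state the intended rule. If either part alone is meant to exclude, replace 'and' with 'and/or' in exclusions 23 and 24, as in exclusion 29, or split each into two criteria.
2. **Table 2.** Reconcile the EBV row with Section 4.2.2, either by adding a numbered criterion for past immunosuppression or by aligning the table with the criteria that exist.
3. **Enrolled patients.** Review the medication history taken at screening (Section 6.2.1) for any previous anti-CD3 or cell-depleting antibody. The programming note to SAP Table 1.09 says that only current medical conditions are available, so the review may have to go to site source records. State the result in the study report, including if it is none. If a case is found, identify the patient in the listings and show the safety, anti-drug antibody and C-peptide results with and without that patient.

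The cost is a few words in two criteria, one alignment in Table 2 and one history check on a small trial. Sample size and the planned models do not change.
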